4.1.9 Crude IRD

The crude IRD will be calculated as the crude incidence rate in the exposed minus the crude incidence rate in the unexposed:

$$IRD = \frac{E_1}{Y_1} - \frac{E_2}{Y_2}$$

with an approximate 95% CI as outlined in Rothman et al. (2008):

$$IRD \pm Z_{0.025} \sqrt{\frac{E_1}{Y_1^2} + \frac{E_2}{Y_2^2}}$$

Where $Z_{0.025}$ is the 2.5th percentile of the standard normal distribution.

All crude IRDs will be reported as point estimates with 95% CIs.

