4.9 Data analysis

Descriptive analyses for all variables of interest will be presented overall and stratified by database.* For categorical variables, frequencies and percentages will be presented for each level. For continuous variables, the mean, standard deviation, minimum, maximum, median, and quartiles will be presented. For estimates, two-sided 95% confidence intervals will be calculated.

* Descriptive and comparative analyses for all variables of interest will be presented overall and stratified by database, with the exception of IUD type. The variable IUD type will be analyzed by database, but only each database holder and RTI-HS will have access to the database-specific information. Data shared with Bayer will only present IUD type aggregated over all data sources. Additionally, analyses for objectives 18 and 26 will be presented by database only if there are more than 20,000 subsequent IUD insertions for the research partner that can be included in the analysis.

Crude incidence rates and cumulative incidence of the outcomes will be estimated for each exposure group (i.e., postpartum IUD insertion time category, breastfeeding status at the time of IUD insertion, type of IUD [LNG vs. copper]).

Crude hazard ratios will be calculated for each outcome without adjustment for covariates within each database. Confounding adjustment will be performed via overlap weighting. Adjusted hazard ratios will be calculated accounting for the propensity score-based weighting approach.

Effect estimates across all data sources will be estimated and presented as the main study results. Effect estimates, except IUD type, will also be presented for each database.

Analyses of the adjusted hazard ratios for the two primary objectives (uterine perforation by breastfeeding status at IUD insertion and uterine perforation by postpartum timing of IUD insertion [in four categories]) combined across all data sources will include hypothesis testing using two-sided statistical tests with a significance level of 0.05 (as requested by the FDA) to test the hypothesis of no difference in the perforation risk between the exposed and referent groups. There will be no adjustment for multiplicity. Statistical tests will be conducted on the assumption that residual confounding can be neglected. However, the validity of this assumption cannot be assessed within the framework of this study.

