9.4.4 Regenstrief Institute

Regenstrief has research access to the Indiana Health Information Exchange, which serves over 17 million patients and includes clinical data from 103 Indiana hospitals, 41 core hospital systems, 60 community clinics, and the state and local public health departments of Indiana. Data from health care encounters are available for this study since 2001 and are captured in a standardized fashion for inpatient admission/discharge information; outpatient visit information; laboratory values; microbiology, pathology, radiology, and cardiology reports; and clinical notes. Data from the datasets are linked via a unique identifier across institutions.

In the validation study, continuous enrollment was measured via health care encounters. Of all IUD insertions in this data source, 74% (~5,700) were in women with at least one clinical encounter 12 months or more before the date of insertion.

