4.1.2 Crude Incidence Rates

Crude incidence rates (I) will be calculated as the number of incident outcomes (E) occurring during the person-time at risk divided by the total person-years at risk (Y).

$$I = \frac{E}{Y}$$

The exact confidence intervals (CIs) will be calculated using the relationship between the Poisson distribution and chi-square distribution as described in Dobson et al. (1991). The lower and upper bounds (LB and UB) of the 95% CI will be calculated as follows:

$$I_{LB} = \max\left(0, \left(\frac{X_{2E,0.025}^2}{2}\right) / Y\right), I_{UB} = \left(\frac{X_{2(E+1),0.975}^2}{2}\right) / Y$$

where $X_{d,\alpha}^2$ represents the α th percentile of the chi-square distribution with d degree of freedom.

Crude incidence rates will be reported as point estimates (number of cases per 1,000 person-years) and 95% CIs.

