6.2.2.3 Comparing Adjusted IRR and Adjusted IRD

To compare results from this study to those obtained in EURAS-IUD, we will estimate the adjusted IRR and IRD of uterine perforation at 1 year and 5 years of follow-up among women who had a first observed IUD insertion ≤ 36 weeks postpartum versus women who had a first observed IUD insertion > 36 weeks postpartum, including women without recorded delivery within the past 52 weeks (objective 17). Adjusted IRRs and IRDs will be calculated via weighted estimation of the rates using overlap weights as described in Sections 4.1.8 and 4.1.10, respectively.

Using the final analysis datasets after propensity score development and weighting, we will calculate adjusted IRRs and IRDs for the study outcomes. Tables will display the weighted number of outcomes, total weighted person-years, and weighted incidence rates for women who had a first observed IUD insertion ≤ 36 weeks postpartum and for women who had a first observed IUD insertion > 36 weeks postpartum. The adjusted IRRs and IRDs along with 95% CIs will be displayed. Analysis Tables 17.1 will be created for uterine perforation.

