Figure 2.1.1 through 2.1.5	Standardized differences in the unweighted and weighted samples		Pooled and by site (5 figures)
Table 2.4	Adjusted HR from Cox model with baseline covariates (sensitivity analysis)	Layout 7	Pooled, including interaction with site (1 table ^b)
Objectives 3 through 12	Crude incidence rate and cumulative incidence by analysis set, postpartum status, breastfeeding status, IUD type, menorrhagia		
Tables 3.1 through 3.5	Crude incidence rate and cumulative incidence	Layout 8	Pooled and by site (5 tables)
Figure 3.1	Kaplan-Meier cumulative incidence plot by analysis set		Pooled (1 figure)
Figure 4.1	Kaplan-Meier cumulative incidence plot by postpartum status		Pooled (1 figure)
Figure 5.1	Kaplan-Meier cumulative incidence plot by breastfeeding status		Pooled (1 figure)
Figure 6.1	Kaplan-Meier cumulative incidence plot by IUD type		Pooled (1 figure)
Figure 7.1	Kaplan-Meier cumulative incidence plot by menorrhagia		Pooled (1 figure)
Objectives 8 through 12	Crude incidence rates and cumulative incidence for IUD expulsion		Same set of tables and figures as objectives 3-7 (5 tables + 5 figures)
Objective 13			
Table 13.1 through 13.5	Prevalence of difficult IUD insertion by exposure and outcome	Layout 9	Pooled and by site (5 tables)
Objective 14	Postpartum period (≤ 14 vs. > 14 weeks) and uterine perforation		Same set of tables and figures as objective 1 excluding Table 1.4 (11 tables + 5 figures)
Objective 15	Postpartum period (≤ 36 vs. > 36 weeks) and uterine perforation		Same set of tables and figures as objective 1 excluding Table 1.4 (11 tables + 5 figures)
Objective 16	IUD type and uterine perforation		Same set of tables and figures as objective 1 excluding Table 1.4 Only pooled results will be reported (3 tables + 1 figures)
Objective 17	Postpartum period (≤ 36 vs. > 36 weeks) and uterine perforation		
Table 17.1	Crude and adjusted incidence rate ratios and differences for uterine perforation at 1 year and 5 years of follow-up	Layout 10	Pooled and by site (1 table)
Objective 18^c	Subsequent insertions for uterine perforation (subsequent insertions)		Same set of tables and figures as objectives 1, 2, 14, 15, 16 excluding Tables 1.4 and 2.4 (47 tables + 21 figures)
Objective 19^d	Menorrhagia and uterine perforation		Same set of tables and figures as objective 1 excluding Table 1.4 (11 tables + 5 figures)

Table/Figure Number	Content	Table Layout ^a	Note

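### The crude rate-difference interval in SAP 4.1.9 gives no variance to a group without events, so at the smallest site the planned 95% interval covers about 86–92% when there is no true difference

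*SAP*

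**What the plan says.** SAP 4.1.9 defines the crude IRD as E1/Y1 − E2/Y2. Its interval, which the SAP calls approximate, is IRD ± 1.96 × √(E1/Y1² + E2/Y2²). There is no rule for zero or small counts, and the section ends: "All crude IRDs will be reported as point estimates with 95% CIs". SAP 4.1.10 applies the same formula to weighted counts for the adjusted IRD.

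The neighbouring measures are handled differently. For the crude rate, SAP 4.1.2 states: "The exact confidence intervals (CIs) will be calculated using the relationship between the Poisson distribution and chi-square distribution". For the crude incidence rate ratio (IRR), SAP 4.1.7 uses Poisson-based limits from the F distribution.

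The IRD is used for objective 17, which compares women with a "first observed IUD insertion ≤ 36 weeks postpartum versus women who had a first observed IUD insertion > 36 weeks postpartum". SAP 9.4 lists Table 17.1 as "Crude and adjusted incidence rate ratios and differences for uterine perforation at 1 year and 5 years of follow-up", pooled and by site, and Table Layout 10 has a block for RI. RI is the smallest source: Protocol 9.4.4 reports that "74% (~5,700) were in women with at least one clinical encounter 12 months or more before the date of insertion".

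The only provision for sparse data is in the introduction to SAP 6. Cells with counts under 10 may be combined, excluded or left alone, as the study team decides when it finds them.

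**The concern.** Perforation is rare and RI is small, so a count of zero among women with early insertion is a realistic result there. The formula then treats the early-insertion rate as known exactly to be zero, and all the uncertainty comes from the other group. The interval becomes too narrow, and with no true difference it misses mostly on one side, towards a lower risk with early insertion. In a postmarketing safety study that is the less welcome direction for a by-site interval labelled 95% to fail.

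**Working it through.** **Plan's own figures.** The documents state no coverage for the IRD interval, so there is nothing to reproduce directly. The risk input was checked against Protocol Table 4, using Schoenfeld power at a hazard ratio of 2.0:
- Breastfeeding: 60,000 × 0.0013 = 78 events; √(78 × 0.6 × 0.4) × ln 2 − 1.96 = 1.04, which gives 85.1% (stated 85%).
- ≤ 6 versus > 52 weeks: 168,750 insertions split 5:70 give 72.6% (stated 73%).

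**Inputs.**
- Risk: 1.3 per 1,000 insertions at 1 year (Protocol 9.5).
- RI size: about 5,700 insertions (Protocol 9.4.4), of which about 90% are first insertions (Protocol 9.5), so 5,700 × 0.9 ≈ 5,100. The upper end of 7,000 assumes that RI grows roughly as the whole study does. The final RI cohort is not stated.
- Share at ≤ 36 weeks: not stated. The 5:20:5:70 allocation in Protocol 9.5 puts it between 25% (≤ 14 weeks) and 30% (≤ 52 weeks); 28% is used as a central value.
- Person-time: one person-year per insertion (assumption).

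**Zero-event property.** With E1 = 0 the upper limit is (−E2 + 1.96√E2)/Y2. This is negative when √E2 > 1.96, that is E2 > 3.84, so from 4 events upward. With E1 = E2 = 0 the interval is (0, 0).

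**Coverage by exact enumeration.** E1 and E2 are independent Poisson counts. The 4.1.9 formula is applied to every pair and the probabilities are summed. With no true difference:

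| First insertions | Share ≤ 36 weeks | Expected events (≤ 36 v > 36 weeks) | Coverage | Wholly below 0 | Wholly above 0 |
|---|---|---|---|---|---|
| 5,100 | 25% | 1.7 v 5.0 | 85.5% | 14.1% | 0.4% |
| 5,100 | 28% | 1.9 v 4.8 | 88.2% | 11.3% | 0.5% |
| 5,700 | 28% | 2.1 v 5.3 | 89.1% | 10.3% | 0.6% |
| 7,000 | 28% | 2.5 v 6.6 | 90.9% | 8.4% | 0.7% |
| 7,000 | 30% | 2.7 v 6.4 | 92.3% | 6.9% | 0.8% |

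In the 5,700 row, P(E1 = 0) = e^(−2.075) = 12.6%, and 9.8 of the 10.3 points below 0 come from E1 = 0.

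**Other sizes, 28% exposed, no difference.** Coverage is 93.8% at 15,000 insertions, 94.8% at 80,000–100,000 and 94.9% at 225,000.

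**True hazard ratio 2.0, overall risk held at 1.3 per 1,000.** Over the same RI range, coverage is about 90–93% and about 1–4% of intervals lie wholly below 0. At 5,700 and 28% the figures are 92.5% and 2.4%.

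**One data set: 0 versus 6 events.** Scaling the site counts in Protocol 9.4 to 225,000 gives RI 225,000 × 5,700/200,700 ≈ 6,390 insertions, where 200,700 = 100,000 + 80,000 + 15,000 + 5,700. At 28%, Y1 = 1,789 and Y2 = 4,601.
- SAP 4.1.9: −6/4,601 = −1.30 per 1,000; half-width 1.96 × √6/4,601 = 1.04; interval −2.35 to −0.26.
- Exact upper limit for the ≤ 36-week rate (SAP 4.1.2): 3.689/1,789 = 2.06 per 1,000. The exact lower limit for the other group is 0.48.
- Combining those limits by MOVER (method of variance estimates recovery), the upper limit is −1.30 + √(2.06² + (1.30 − 0.48)²) = 0.92. The lower limit is −2.84.
- IRR upper limit with the upper 2.5% F point: (4,601/1,789) × (1/6) × 5.096 = 2.18, so that interval includes 1.

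**Alternatives at RI, same range, no difference.** A score interval covers 95.1–96.2%; MOVER covers 97.8–98.7%.

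**The case against.** The strongest reply is that the reach is narrow. The affected result is mainly the 1-year perforation IRD at one site, under one secondary objective. Formal testing is confined to the two primary adjusted hazard ratios. Layout 10 prints no P value for the IRD, and it shows events and person-years above each interval, so a reader can see a zero cell. The SAP also calls the interval approximate. All of this stands, and it is why the point ranks low. It does not make a 95% label correct at 86–92% coverage.

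A second reply is the sparse-cell clause, since RI's expected counts of about 2 and 6 both fall under its threshold of 10. The clause could lead the team to drop the RI cell. But it is discretionary, it allows the cell to be left unchanged, and it does not alter how the interval is computed.

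A third reply is that the coverage range is not in the documents. That is correct. With a ≤ 36-week share of 20%, coverage would be about 79–84%; with 8,000–10,000 first insertions at RI and a share of 28–30%, it would be 92–94%.

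A reader might infer four stronger things that the documents do not support:
- *That the interval tends to call early insertion safer even when it raises the risk.* At a true hazard ratio of 2.0 only about 1–4% of RI intervals lie wholly below 0.
- *That the pooled IRD is unreliable.* Its coverage is about 95%.
- *That the expulsion IRD (objective 25) fails in the same way.* The documents give no expulsion risk from which to calculate this, and at an assumed 5 per 1,000 RI coverage is already 94.5%.
- *That the SAP as printed necessarily yields an IRR interval that contradicts the IRD interval.* The 2.18 above uses the upper 2.5% point of F. SAP 4.1.7 prints the 2.5th percentile, which read literally gives an upper limit of about 0.01. The contrast holds only if the upper point is intended.

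**Conclusion.** The point holds for by-site reporting at the smallest source. The zero-variance behaviour is a matter of algebra and needs no assumption. The size, 86–92% coverage with roughly 7–14% of intervals wholly below 0 under no difference, rests on the assumed RI cohort, ≤ 36-week share, perforation risk and follow-up. The primary analyses and the conclusions drawn from pooled data do not depend on it. It is worth correcting because the SAP already specifies exact limits for the rates that make up the difference.

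**What to change.** In SAP 4.1.9, prespecify for the crude IRD a score interval (Miettinen–Nurminen type) for a difference of two Poisson rates. Alternatively, use MOVER with the exact limits from 4.1.2, which is simpler to program but conservative. A further option is to state a minimum event count below which by-site IRD intervals are not shown.

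SAP 4.1.10 takes its interval from 4.1.9 by cross-reference, so it must be amended at the same time. Otherwise the adjusted IRD would inherit Poisson limits for weighted, non-integer counts. When 4.1.7 is next edited, the F percentile should be clarified as well.

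The cost is a change to two SAP sections and a few lines of code, with no new data. Intervals at RI become clearly wider when counts are near zero: for 0 versus 6 events the MOVER width is 0.92 + 2.84 ≈ 3.8 per 1,000, against 2.35 − 0.26 ≈ 2.1 now. Pooled intervals barely change.

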4.1.10 Adjusted IRD Via Weighting

The IRD will be adjusted for possible confounding effects via weighted estimation of the rates using overlap weights (Section 4.1.5) derived from the same propensity score models as those developed for adjustment of the hazard ratios. The adjusted IRD will be calculated as the weighted incidence rate in the exposed minus the weighted incidence rate in the unexposed.

$$IRD_w = \frac{E_{w1}}{Y_{w1}} - \frac{E_{w2}}{Y_{w2}}$$

The 95% CI of IRD_w will be calculated as described in Section 4.1.9 using the number of weighted incident outcomes and weighted person-years.

4.2 Handling of Loss to Follow-Up and Premature Discontinuation

This is a retrospective study. To minimize use of records with incomplete data for baseline covariates, women will be required to have 12 months of continuous enrollment within the data source prior to the index date. Additionally, at the Kaiser Permanente sites, censoring will occur if more than 31 days passes without insurance coverage sufficient to maintain enrollment.

This study will be conducted using data from four health care systems with EHRs: KPNC, KPSC, KPWA, and RI. Date of disenrollment from the database, that is, the date on which a woman is no longer enrolled in an eligible insurance plan, will be captured by KPNC, KPSC, and KPWA. For RI, date of last clinical encounter—the last date on which a woman has an in-person encounter that is recorded in the database—will be captured. The dates of disenrollment and last clinical encounter will be used as stopping dates for person-time at risk.

4.3 Handling of Missing Data

Missing data will be treated as missing, unless specified otherwise, and no imputations will be performed. In database analyses of previously collected data, if information on a particular binary variable, such as a disease diagnosis or a medication, is available in the database, patients are assumed to have the factor only if there is evidence for its presence (i.e., absence of information will be taken to mean absence of the condition or medication).

Where appropriate, variables will include a “missing” category for analyses. Consequently, data analyses will be conducted using all women and insertions to the extent possible with respect to their observed available data (i.e., the IUD insertion will not be included in an analysis if missing data for any variable in that analysis, except where “missing” is a separate category for the analysis).

Counts of missingness will be reported in descriptive analysis of categorical variables, and percentages for the nonmissing categories will be based on the number of nonmissing values. For continuous variables, the number of nonmissing values will be reported, and descriptive summaries

will be based on the number of nonmissing values. In addition, the percentage of patients or insertions with missing data will be provided for breastfeeding and IUD type.

4.4 Interim Analyses and Data Monitoring

No interim analyses are planned. Data monitoring is not applicable in this retrospective cohort study based on secondary use of EHR data.

4.5 Data Rules

The index date will be the date of the IUD insertion. In the primary analyses, only the first eligible IUD insertion will be considered; all subsequent IUD insertions will be included in secondary analyses (objectives 18 and 26). Baseline characteristics will be assessed for each eligible insertion. The look-back time will consist of all available data on or before the index date, unless otherwise specified for a particular variable in Section 4.6. Because all insertions included in the study are required to have at least 12 months of data before the index date, a minimum of 12 months of data from which to evaluate baseline characteristic values will be available. For some insertions, more information will be available, and all information within the database on or prior to the index date will be considered to reduce misclassification of baseline information.

4.6 Definition of Derived Variables and Subgroups

The variables described in Table 1 will be derived by RTI-HS using the data provided by the four research sites. Since the unit of observation in the data provided by the research partners will be an IUD insertion, these variables will be calculated for each insertion and included in the final dataset. If a woman has more than one eligible insertion in the dataset, the variables will be derived for each insertion using data relevant to that insertion.

Table 1. Definition of Derived Variables

Variable	Definition ^a
Baseline covariates	
IUD insertion count	The number of eligible IUD insertions for the woman as of the index date (including the index insertion). IUD insertion count increases by 1 each time a new index date is identified for the woman
Initial IUD insertion	Indicator variable: If IUD insertion count = 1 then initial IUD insertion = 1 If IUD insertion count > 1 then initial IUD insertion = 0
Difficult insertion	Indicator variable: 1 = Yes if any of the following occur on the index date (or in 7 days before index date for misoprostol): cervical dilation, ultrasound guidance, paracervical block, provider note, use of misoprostol 0 = No if none of the above indicators of difficult insertion are found on the index date
Age tertile	Categorical variable for age based on tertiles (or closest integer cut point [i.e., in years]) for all ages at all first index dates observed within the data
Duration of look-back period	Derived number of days, starting on the date of start of enrollment or first clinical encounter in the EHR database and ending on the index date Duration of look-back period is calculated for each index date
Categorical indicator for provider number of insertions in previous year	Indicator variable: 0 = fewer than 50 provider number of IUD insertions in the 365 days prior to and on the index date, 1 = 50 or more provider number of IUD insertions in the 365 days prior to and on the index date
Provider annualized number of insertions in previous year	Provider number of IUD insertions in previous year divided by provider length of employment in previous year , multiplied by 365
Concomitant gynecological procedure	Indicator variable: 1 = Yes if any of the following procedures occurred on the index date: abortion, aspiration and curettage, dilation and curettage, excision/biopsy of cervix or uterus, ablation, colposcopy and other cervical procedures, hysteroscopy, laminaria, laparoscopy, lysis adhesions, myomectomy, nerve procedure, salpingectomy/oophorectomy 0 = No if none of the above procedures occurred on the index date
Exposures	
Postpartum number of days	Number of person-days, starting on the most recent pregnancy delivery date prior to or on the index date and ending on the index date . There will be a derived postpartum number of days associated with each insertion for each woman. This variable will range from 0 to 365 days and will be missing if the most recent pregnancy delivery date is not recorded or is more than 365 days before the index date .
Postpartum—14-week, dichotomous	Indicator variable: * If postpartum number of days ≤ 98, then postpartum—14-week, dichotomous = 1 * If postpartum number of days > 98 or missing, then postpartum—14-week, dichotomous = 0

Variable	Definition ^a
Postpartum—36-week, dichotomous	Indicator variable: * If postpartum number of days ≤ 252 , then postpartum—36-week, dichotomous = 1 * If postpartum number of days > 252 or missing, then postpartum—36-week, dichotomous = 0
Postpartum—categorical	Categorical variable: * If postpartum number of days ≤ 42 , then postpartum—categorical = 1 (6 weeks or less) * If postpartum number of days > 42 and ≤ 98 , then postpartum—categorical = 2 (> 6 to ≤ 14 weeks) * If postpartum number of days > 98 and ≤ 365 , then postpartum—categorical = 3 (> 14 to ≤ 52 weeks) * If postpartum number of days > 365 or missing, then postpartum—categorical = 0 (> 52 weeks or no delivery)
Outcomes	
Person-time at risk (days, i.e., time to event/censor)	Number of person-days, starting on the index date of IUD insertion and ending on the earliest of date uterine perforation confirmed , date IUD expulsion confirmed , or censoring date . A derived number for person-time at risk will be associated with each IUD insertion for each woman.
Uterine perforation event indicator	Indicator variable: 0 = No date of uterine perforation confirmed during the person-time at risk 1 = Yes, date of uterine perforation confirmed during the person-time at risk
IUD expulsion event indicator	Indicator variable: 0 = No date of IUD expulsion confirmed during the person-time at risk 1 = Yes, date of IUD expulsion confirmed during the person-time at risk
Other parameter	
Continuous enrollment	For KPNC, KPSC, and KPWA: Number of days from the latest of beginning date of the study period or date of start of most recent enrollment before the index date to the earliest of end date of study period or date of most recent disenrollment following the index date . See illustration in Section 9.6. For RI: Number of days from the latest of beginning date of the study period or date of first clinical encounter to the earliest of end date of study period or date of last clinical encounter following the index date .

EHR = electronic health record; IUD = intrauterine device.

^a Variables in *Italic*, if not defined in this table, are defined in Sections 3.1-3.8.

5 Analysis Sets

